#### **8.4 Reporting Serious Adverse Events**

SAE information must be faxed or e-mailed within 24 hours of becoming aware of the event. The minimum *initial* information required to be reported on the Serious Adverse Event Form is: the protocol number, site number, subject number, subject initials, the event, the causality, the date of the event and the name and contact information (email, phone number) of the person reporting the event. This initial report should be promptly followed up with a *completed* Serious Adverse Event Form.

**Serious Adverse Events:** [name]., M.S.

[contact]

Email: [[contact]](mailto:[contact])

The initial information must include a causality assessment that is provided by the primary Investigator or other medically qualified individual. The causality assessment can be amended as more information is available. Significant new information about ongoing SAEs should be reported promptly to the Sponsor.

Serious adverse events will be evaluated by the Medical Monitor within 24 hours of receipt and plans for management and further reporting (i.e. FDA) determined.

It is the responsibility of the CRO, Integrium, LLC® to promptly notify the other Investigators involved in this study and they in turn notify their respective IRBs about serious and unexpected SAEs for which there is a reasonable possibility of their being related to the investigational product.

#### **Follow-up of Serious Adverse Events**

All follow-up reports will be subject to the same reporting timelines as the Initial Reports. Within 24 hours of receipt of new information, the updated follow-up SAE form, along with any supporting documentation (e.g., subject discharge summary or autopsy reports), should be faxed or emailed to the Sponsor.

#### **8.5 Discontinuation Due to an Adverse Event**

The Sponsor must be notified within 5 days if any subject is withdrawn or discontinues study product use due to an adverse event if AE is related to the study product (see title page for contact information).

#### **8.6 Exposure *in utero* (Pregnancy)**

If a female subject becomes pregnant during the study, study product must be discontinued immediately and she must be followed through the pregnancy and delivery. The Investigator should report the event to the Sponsor immediately as described in [Section 8.4](#) above and complete a pregnancy surveillance form. The expected date of delivery or expected date of the end of the pregnancy should be included in this information. The Investigator is instructed to contact the subject every 3 months until the end of her pregnancy and report the outcome to the

Sponsor. Details of the pregnancy, delivery and health of the infant should be recorded on a pregnancy surveillance form.

The following outcomes of pregnancy fall under the criteria for serious adverse events and should be reported as such: delivery complications prolonging hospitalization, spontaneous abortion, still birth, death of newborn baby, congenital anomaly, and anomaly in a miscarried fetus.

## **9 DATA HANDLING AND RECORD KEEPING**

### **9.1 Confidentiality**

Information about study subjects will be kept confidential and managed according to the requirements of the Health Insurance Portability and Accountability Act. This regulation requires a signed authorization informing the subject of the following:

- What protected health information (PHI) will be collected from subjects in this study
- Who will have access to that information and why
- Who will use or disclose that information
- The rights of a research subject to revoke the authorization for use/disclosure of subject's PHI
- Expiration of authorization

In the event that a subject revokes authorization to collect and use PHI, the Investigator, by regulation, retains the ability to use all information collected prior to the revocation of authorization. For subjects that have revoked authorizations to collect and use PHI, attempts should be made to obtain permission to collect at least vital status (i.e. that the subject is alive) at the end of their scheduled study period.

### **9.2 Source Documents**

Investigators must keep accurate separate records (other than CRFs) of all subject visits which include all pertinent study related information including original signed/dated informed consent forms. Source documents for this study include all written records of study data. All study data must have a paper source document including Investigator assessments.

### **9.3 Screening/Enrollment Log**

A Subject Screening/Enrollment Log, noting reasons for screen failure where applicable, must be maintained for all subjects who are consented. The log should also include subject initials, screening date, subject number, and date of visit.

### **9.4 Case Report Forms**

All data requested on the CRF must be recorded on source documentation. The CRF cannot be the source document for any data. Detailed instructions and training for completing the CRF will be provided to the sites.

Study subjects are not to be identified by name on CRFs, but rather by coded identifiers (subject number and initials). The Investigator or Sub-investigator must review all CRF pages for each subject and approve the group of CRFs pages for each subject.

## 9.5 Data Capture

Study data will be entered into and maintained in a 21 CFR Part 11 compliant database.

## 9.6 Archiving of Study Documentation

The Investigator must retain study records for 2 years following the date a marketing application is approved for the investigational product; or, if the application is not filed or is not approved, until 2 years after the investigation is discontinued and the FDA is notified.

The Sponsor will inform the Investigator, in writing, as to when these documents no longer need to be maintained.

All study documents, original source documents, correspondence, IRB documents, etc. are subject to Sponsor and FDA inspection at any time.

## 10 MONITORING AND DATA QUALITY ASSURANCE

Only persons who are appropriately trained and who have the scientific and clinical knowledge to adequately monitor the study will be selected for monitoring this study. The monitor must have at least one year previous experience in monitoring clinical studies. The monitor should be familiar with the etiology and signs and symptoms of Actinic Keratosis and the treatment options that are currently available.

Before study initiation, the Investigator and site personnel will receive protocol training from the Sponsor's representatives to ensure collection of accurate, consistent, complete and reliable data. This training will take place either at an Investigator Meeting or individually on-site.

During the course of the study, a monitor will make multiple site visits to check the progress of the study, review consent forms, review protocol compliance, assess drug accountability, and ensure that the study is being conducted according to the protocol and Good Clinical Practice. Any review of the subjects' original medical records will be performed in a manner to ensure that subject confidentiality is maintained. The Investigator will ensure that the monitor or other compliance auditor is given access to all study-related documents and has adequate time and space to conduct the monitoring visit including availability of the Investigator and site personnel to discuss findings.

Data capture methods will be designed to ensure accurate transfer of data to electronic media.

The Sponsor's Quality Assurance representative will conduct QA audits randomly or if needed at 5-10% of the investigational sites.

## 11 STATISTICAL CONSIDERATIONS

### 11.1 Sample Size

The sample size estimation of this trial is based on the assumption that the Active product exhibits a complete clearance of the AK lesions in 45% of the subjects, while the Vehicle does so in 20% of the subjects (a difference of 25% between the Active and Vehicle treatment groups). Assuming a power of 80% and  $\alpha$  of 0.05, in order to demonstrate the statistical significance of such an effect difference, 54 patients per treatment group would be needed.

---

Considering the exploratory dose-response character of the trial, and assuming a drop-out rate of 10%, 60 subjects need to be recruited in each treatment group. With 4 treatment groups in the study, it is planned to recruit approximately 240 subjects in the study.

## 11.2 Analysis Data Set

### 11.2.1 Intent to Treat

The intent-to-treat population (ITT) will be the primary efficacy analysis data set and consists of all subjects who are randomized and dispensed study medication.

Missing data for efficacy analysis will be replaced using last observation carried forward (LOCF). If a subject withdraws early from the study, that subject's efficacy assessments captured at the early termination visit will be assigned to the nearest corresponding scheduled visit that has been missed.

### 11.2.2 Per Protocol

The PP population will include all subjects in the ITT population who complete the Week 16 evaluation without any major protocol violations (i.e., any subject or Investigator activity that could have possibly interfered with the therapeutic administration of the treatment or the precise evaluation of treatment efficacy).

Specifically, the PP population will include subjects in the ITT population who meet all of the following criteria:

1. Subject met all inclusion/exclusion criteria.
2. Subject did not take any prohibited concomitant medications during the evaluation period. The concomitant medication usage will be reviewed during the population determination review, remaining blinded to treatment designation, to determine prohibited medication usage that warrants exclusion from the PP population if they met the entry criteria without any protocol violations. This review will take into consideration the timing, duration of treatment with the concomitant medication, and influence on the efficacy and safety assessments prior to deeming a prohibited concomitant medication as a protocol violation that warrants exclusion from PP.
3. Completed the Week 16 visit within the allowed window.
4. Subject was compliant with the dosing regimen. A subject will be considered compliant if the subject applied at least 80%, but no more than 120% of the expected number of applications during the entire treatment period.

Subjects who prematurely discontinue from the study due to documented lack of efficacy, worsening condition, or a treatment-related AE will be included in the PP population. These subjects will be considered failures for all subsequent visits in the analysis of the primary and secondary endpoints of complete and partial clearance. Other than this, no imputations for missing data will be made for the PP populations.

Other additional criteria may be added to the list to accommodate for unforeseen events that occurred during the conduct of the trial that result in noteworthy study protocol violations. These criteria will be documented with appropriate signature at the time subject populations are finalized, prior to database lock.

### 11.2.3 Safety Population

All subjects who receive at least one confirmed dose of study product and provide any post-baseline safety information will be included in the safety population. No imputation will be made for missing safety data.

### 11.3 Demographic and Baseline Data

Subject demographic and baseline data characteristics will be reported in descriptive summaries by treatment group for the Intent to Treat, Per Protocol and Safety populations.

### 11.4 Efficacy Analyses

Efficacy summaries will be provided for the Intent to Treat and Per Protocol populations.

Descriptive statistics (N, arithmetic means, SD, minimum, median, maximum) for all continuous values and frequency tables for categorical variables will be created. With regard to primary and secondary objectives as descriptive statistical evaluation, absolute and relative frequencies of number of observations will be presented together with 95 %- confidence intervals.

In case of missing values the last-observation-carried forward principle shall be applied.

A statistical testing procedure Chi-Quadrat test or alternatively a binomial testing procedure will be applied. In case of small sample sizes alternatively Fisher's exact test may be applied. Other tests may be applied as required and these will be enumerated in the Statistical Analysis Plan (SAP).

Further details of the statistical evaluation procedure will be presented in the Statistical Analysis Plan (SAP). Analysis sets (ITT population, safety population, per-protocol population, rational for exclusion from any population) will also be specified in the SAP.

#### Primary endpoint

For statistical assessment of the primary endpoint with a significance level of 0.05% the following underlying hypotheses are used:

$H_0: p_1 \leq p_2$  vs.  $H_1: p_1 > p_2$

where  $p_1$  is the treatment effect of 2.5% DFD-07 (celecoxib) Cream twice daily and  $p_2$  is the treatment effect of the Vehicle Cream preparation.

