#### Secondary endpoints

For statistical assessment of all product comparisons after certain period of treatment (i.e. at Visits 3, 4, 5 and 6) with a significance level of 0.05% the following underlying hypotheses are used:

$H_0: p_1 \leq p_2$  vs.  $H_1: p_1 > p_2$

where  $p_1$  is the treatment effect of 1.25% or 2.5% DFD-07 (celecoxib) Cream once daily and  $p_2$  is the treatment effect of the Vehicle Cream preparation.

For product and time point comparisons of medians, Mann-Whitney U-test and Wilcoxon-test may be applied.

---

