2.6. Efficacy

Primary endpoint

For statistical assessment of the primary endpoint with a significance level of 0.05 the following underlying hypotheses are used:

$H_0: p_1 \leq p_2$ vs. $H_a: p_1 > p_2$

Where p_1 is the treatment effect of 2.5% DFD-07 (celecoxib) Cream twice daily and p_2 is the treatment effect of the Vehicle Cream preparation.

Secondary endpoints

For statistical assessment of all product comparisons after certain period of treatment (i.e. at Visits 3, 4, 5 and 6) with a significance level of 0.05, the following underlying hypotheses are used:

$H_0: p_1 \leq p_2$ vs. $H_a: p_1 > p_2$

Where p_1 is the treatment effect of 1.25% or 2.5% DFD-07 (celecoxib) Cream once daily and p_2 is the treatment effect of the Vehicle Cream preparation.

For the percent change from baseline in AK lesion counts, the Mann-Whitney U-test (Wilcoxon rank sum test) will be used to test for treatment differences compared to the Vehicle Cream preparation at a significance level of 0.05.

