2.8. Sample Size and Power Considerations

The sample size estimation of this trial is based on the assumption that the Active product exhibits a complete clearance of the AK lesions in 45% of the subjects, while the Vehicle does so in 20% of the subjects (a difference of 25% between active and Vehicle treatment groups). Assuming a power of 80% and α of 0.05, in order to demonstrate the statistical significance of such an effect difference, 54 patients per treatment group would be needed.

Considering the exploratory dose-response character of the trial, and assuming a drop-out rate of 10%, 60 subjects need to be recruited in each treatment group. With 4 treatment groups in the study, it is planned to recruit approximately 240 subjects in the study.

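### Protocol 11.4 writes the significance level as 0.05% where the sample size and the SAP use 0.05: almost certainly a slip, but it should be corrected and the sidedness stated with it

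*Protocol*

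**What the plan says.** Protocol 11.4 gives the level for the primary endpoint as 0.05%: "For statistical assessment of the primary endpoint with a significance level of 0.05% the following underlying hypotheses are used". The paragraph on secondary endpoints has the same figure: "with a significance level of 0.05% the following underlying hypotheses are used". The general part of the same section plans 95% confidence intervals.

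Protocol 11.1 sizes the trial on an expected vehicle clearance rate of 20% and, for the active arm, this assumption: "the Active product exhibits a complete clearance of the AK lesions in 45% of the subjects". Power is set at 80% and alpha at 0.05, and the result is given as "54 patients per treatment group would be needed". A 10% drop-out allowance brings this to 60. SAP 2.8 repeats the calculation: "Assuming a power of 80% and α of 0.05, in order to demonstrate the statistical significance".

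SAP 2.6 carries the protocol's sentence without the percent sign: "For statistical assessment of the primary endpoint with a significance level of 0.05 the following underlying hypotheses are used". It gives 0.05 again for the secondary endpoints and for the Mann-Whitney test of percent change in lesion count.

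In both documents the hypotheses are directional: the null is p1 ≤ p2 and the alternative is p1 > p2. Neither sample size section says whether its alpha is one-sided or two-sided.

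**The concern.** The two documents give thresholds for the same primary test that differ by a factor of 0.05 / 0.0005 = 100, and the protocol also disagrees with its own sample size section. The SAP does not mention the difference, and neither document says which prevails.

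A significance level is a decision rule fixed in advance, and a reader should not have to infer it. If the discrepancy is first noticed after unblinding, the move from the protocol's written figure to the SAP's looks like a hundredfold loosening of the primary criterion, and the sponsor would have to argue intent after the fact. The range in dispute is not remote: as shown below, a result exactly at the planning assumption falls inside it.

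**Working it through.** **Inputs.** Response rates of 0.45 and 0.20, 80% power, alpha 0.05, 54 per arm before drop-out and 60 after (Protocol 11.1, SAP 2.8); equal allocation (Protocol 6.5); Pearson chi-square, with Fisher's exact test if any cell is below 5 (SAP 2.1). Sidedness is not stated for the sample size, so both are computed.

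**Step 1: reproduce the plan's figure.** The pooled-variance formula without continuity correction is

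n = [z(α)·√(2p̄q̄) + z(power)·√(p1q1 + p2q2)]² / (p1 − p2)²

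Here p̄ = (0.45 + 0.20)/2 = 0.325, so √(2 × 0.325 × 0.675) = 0.6624. Also √(0.45 × 0.55 + 0.20 × 0.80) = √0.4075 = 0.6384.

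- Two-sided 0.05: (1.960 × 0.6624 + 0.8416 × 0.6384)² / 0.0625 = 53.9, so 54. This matches the plan.
- One-sided 0.05: (1.645 × 0.6624 + 0.8416 × 0.6384)² / 0.0625 = 42.3, so 43. This does not match.
- With continuity correction: 62 two-sided, 51 one-sided. Neither matches.
- Drop-out: 54 / 0.90 = 60. This matches.

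**Step 2: power under each reading.** Power = Φ{[0.25·√n − z(α) × 0.6624] / 0.6384}. For example, at n = 54 and two-sided 0.0005 (z = 3.481) this is Φ[(1.837 − 2.306)/0.6384] = Φ(−0.734) = 23.2%.

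| Level | Sides | 54 per arm | 60 per arm | n per arm for 80% |
|---|---|---|---|---|
| 0.05 | two | 80.1% | 84.1% | 54 |
| 0.05 | one | 87.9% | 90.8% | 43 |
| 0.0005 | two | 23.2% | 28.2% | 130 |
| 0.0005 | one | 29.6% | 35.2% | 119 |

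Exact binomial enumeration of the Pearson test at 0.0005 gives 23.7% (54 per arm, two-sided) to 35.9% (60 per arm, one-sided). Fisher's exact test gives 18.2% to 29.4%.

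**Step 3: a result at the planning assumption.** Take 27/60 against 12/60, which is 45% against 20%. The pooled rate is 39/120 = 0.325, the standard error is √(0.325 × 0.675 × 2/60) = 0.0855, and z = 0.25/0.0855 = 2.92. The p-value is 0.0035 two-sided or 0.0017 one-sided. Either is below 0.05 and above 0.0005, so the SAP would call it a success and the protocol, read literally, a failure.

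**Step 4: which level is meant.** Protocol 11.1, SAP 2.8, all three statements in SAP 2.6 and the 95% intervals in Protocol 11.4 point to 0.05. An interval matching a two-sided 0.0005 test would be 99.95%. Nothing in either document explains or defends 0.0005.

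**The case against.** The strongest reply is that this is an evident slip which the working document already has right. The protocol leaves further statistical detail to the SAP (11.4) and describes the SAP as covering all analyses (11.7). SAP 2.6 gives 0.05, and the protocol itself calls the trial exploratory in its sample size section. An analyst following the SAP would never apply 0.0005.

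Most of this stands. A reader might infer from the power table that the trial is badly underpowered. The documents do not support that: the design is sized for two-sided 0.05 and reaches 80-84% power there, and the figures of 23-35% describe only what the protocol's sentence would mean if applied to the letter. Nor do they extend to the secondary endpoints. They rest on 45% against 20%, and the plan gives no separate effect size for the once-daily arms, the earlier visits, partial clearance or percent change.

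What the reply does not dispose of is the text. Deferring detail to the SAP is not the same as letting it replace a threshold that the protocol states, and the SAP does not say that it does so.

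A reader might also suppose that deleting the percent sign settles the matter. It does not: 0.05 attached to one-sided hypotheses is not the level that gives 54 per arm.

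**Conclusion.** The contradiction is real and sits on the primary decision rule, within the protocol and between the protocol and the SAP. It is a drafting error, not a design failure, and its practical weight is limited because the SAP already uses 0.05. The loss of power to 23-35% is conditional on a literal reading, on 45% against 20%, and on 54 to 60 per arm; the range covers both choices of sidedness under the pooled-variance formula.

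The ambiguity that survives into the SAP is sidedness. At 54 per arm the stated 80% power belongs to two-sided 0.05, equivalent to one-sided 0.025. Testing the written hypotheses at one-sided 0.05 would give 87.9% power at 54 per arm, and a one-sided p-value between 0.025 and 0.05 would pass under one reading and fail under the other.

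**What to change.** In both endpoint paragraphs of Protocol 11.4, replace 0.05% with 0.05. If the protocol is not to be amended, add a sentence to SAP 2.6 before unblinding, stating that 0.05 replaces the 0.05% printed in the protocol.

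In the same correction, state the sidedness that matches the sample size: two-sided 0.05, or equivalently one-sided 0.025 if the directional hypotheses are kept. Put the same words in Protocol 11.1, Protocol 11.4, SAP 2.6 and SAP 2.8 so that all four places carry one threshold.

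The cost is a few words in an amendment or one or two sentences in the SAP. It needs no additional subjects, data or analyses.

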#### Secondary endpoints

For statistical assessment of all product comparisons after certain period of treatment (i.e. at Visits 3, 4, 5 and 6) with a significance level of 0.05% the following underlying hypotheses are used:

$H_0: p_1 \leq p_2$  vs.  $H_1: p_1 > p_2$

where  $p_1$  is the treatment effect of 1.25% or 2.5% DFD-07 (celecoxib) Cream once daily and  $p_2$  is the treatment effect of the Vehicle Cream preparation.

For product and time point comparisons of medians, Mann-Whitney U-test and Wilcoxon-test may be applied.

---

## 11.5 Safety Analyses

All subjects who receive at least one dose of study product and provide any post-baseline safety information will be included in the Safety analysis.

### 11.5.1 Extent of Exposure

The extent of exposure to study product will be summarized as the total number of applications and the total amount of study product used based on tube weights. The amount of the last dose will be provided based on tube weight before and after treatment. Also the calculated mean amount of drug used per application will be provided.

### 11.5.2 Local Safety Evaluation

Erythema, edema, weeping/exudate, flaking/scaling/dryness, scabbing/crusting, erosion /ulceration and vesiculation/blistering will be summarized by visit.

